Table 11 Suggested therapy for diarrhea	31

LIST OF ABBREVIATIONS

Term	Definition
AE	Adverse Event
ALT	Alanine aminotransferase
AML	Acute myeloid leukemia
AST	Aspartate aminotransferase
AUC	Area under the curve
BID	Twice daily
CBC	Complete blood count
C _{max}	Maximum concentration of drug in serum
CMP	Complete metabolic panel
CR	Complete remission
CRi	Complete remission with incomplete count recovery
CRF	Case report form
CTCAE	Common terminology criteria for adverse events
DARF	Drug accountability record form
DLT	Dose limiting toxicity
DoR	Duration of response
EC	Ethics Committee
ECOG	Eastern Cooperative Oncology Group
eCRF	Electronic case report form
EFS	Event-free survival
EKG	Electrocardiogram
EOS	End of study
FLAG	Fludarabine, Ara-C, G-CSF
FLT3	FMS-like tyrosine kinase 3
FLT3-ITD	FMS-like tyrosine kinase 3 – internal tandem duplication
FLT3-TKD	FMS-like tyrosine kinase 3 – tyrosine kinase domain
GCP	Good clinical practice
GVHD	Graft versus host disease
HAM	High-dose cytarabine and mitoxantrone
HiDAC	High-dose cytarabine
HR	Hazard ratio
HSCT	Hematopoietic stem-cell transplant
IB	Investigator Brochure

ICF	Informed consent form
ICH	International Conference on Harmonisation
Ida	Idarubicin
IDAC	Intermediate-dose cytarabine
IMP	Investigational medicinal product(s)
IRB/IEC	Institutional review board/ Independent ethics committee
ITT	Intent-to-treat
IVRS	Interactive voice response system
KM curve	Kaplan-Meier curve
LFT	Liver function test
MEC	Mitoxantrone, Etoposide, Cytarabine
MTD	Maximum tolerated dose
MTZ	Mitoxantrone
ORR	Overall response rate
OS	Overall survival
PD	Progressive disease
PDGFR α	Platelet-derived growth factor receptor alpha
PFS	Progression-free survival
PK	Pharmacokinetic
PR	Partial response
PS	Performance Status
RECIST	Response Evaluation Criteria In Solid Tumors
RFS	Relapse-free survival
R/R	Relapsed/Refractory
RR	Response Rate
RTK	Receptor tyrosine kinase
SAE	Serious adverse event
SD	Stable disease
SOC	Standard of care
SUSAR	Suspected Unexpected Serious Adverse Reactions
$t_{1/2}$	Half-life
TID	Three times daily
TKI	Tyrosine kinase inhibitor
t_{max}	Time that drug is at maximum concentration in serum
QD	Once daily

ULN	Upper limit of normal
WOCBP	Women of child-bearing potential

DEFINITION OF TERMS

Term	Definition
Adverse Drug Reaction	Any adverse event that is deemed to be at least possibly related to the study drug.
Audit	A systematic and independent examination of the trial-related activities and documents to determine whether the evaluated trial-related activities were conducted, and the data were recorded, analyzed, and accurately reported according to the protocol, applicable standard operating procedures (SOPs), good clinical practice (GCP), and the applicable regulatory requirement(s).
Case Report Form (CRF)	Sometimes referred to as clinical report form: a printed or electronic form for recording study participants' data during a clinical study, as required by the protocol.
Compliance	Adherence to all the trial-related requirements, good clinical practice (GCP) requirements, and the applicable regulatory requirements.
Consent	The act of obtaining informed consent for participation in a clinical trial from subjects deemed eligible or potentially eligible to participate in the clinical trial. Individuals entered into a trial are those who sign the informed consent document directly or through their legally acceptable representatives.
Enrolled Subject	An enrolled subject is a subject who has signed the informed consent form, completed all screening evaluations, has been deemed eligible for the trial by the investigator and sponsor and has been enrolled.
Ethics Committee	All appropriate properly constituted committees or boards recognized by the appropriate regulatory agencies for approving clinical studies. Including the independent ethics committee and institutional review boards.
Investigator	A person responsible for the conduct of the clinical trial at a trial site. If a trial is conducted by a team of individuals at a trial site, the investigator is the responsible leader of the team and may be called the principal investigator.
Institutional Review Board/ Ethics Review Board (IRB/ERB)	A board or committee (institutional, regional, or national) composed of medical and nonmedical members whose responsibility is to verify that the safety, welfare, and human rights of the subjects participating in a clinical trial are protected.
Regulation	All appropriate regulations, laws and guidelines.
Screening Period	The screening period begins when the subject signs the Informed Consent Form and continues until randomization.
Screen Failure	A screen failure refers to subjects who have signed the Informed Consent Form but do not subsequently enroll in the trial. Data from these subjects will be recorded in the screening log, but not entered into the study database.
Treatment period	The time period from administration of the first dose of study drug through the end of the one month post-treatment discontinuation visit.

[figure not shown]
1. SYNOPSIS

Name of Investigational Product Crenolanib Besylate
Title of Study Pilot study of Crenolanib Combined with Standard Salvage Chemotherapy in Subjects with Relapsed/Refractory Acute Myeloid Leukemia
Version and Date of Protocol Version 3.0, June 7, 2016
Planned number of subjects and investigational sites Approximately 72 subjects (~24 in each cohort) will be enrolled across approximately 10 sites in the U.S.

Study Rationale Treatment of newly-diagnosed acute myeloid leukemia (AML) with standard chemotherapy regimens, such as anthracyclines and cytarabine, can lead to high complete remission (CR) rates (ranging from 60-70%). Unfortunately, the majority of these patients will relapse.
 
Upon relapse, the prognosis for a second remission or response in these patients significantly worsens. Currently, patients who are refractory or relapsed following standard induction therapy have no standardized treatment options. Several combinations have been suggested and each achieve similar outcome. High-dose cytarabine combined with mitoxantrone (HAM) has been shown to be associated with high CR rates in relapsed/refractory (R/R) AML. Two additional aggressive salvage chemotherapies, as per National Comprehensive Cancer Network (NCCN) guidelines, are also common options for relapsed/refractory patients: the combination of mitoxantrone, etoposide, and cytarabine (MEC) and the combination of fludarabine, cytarabine, G-CSF and idarubicin (FLAG-Ida). However, it has been proven difficult to achieve full prolonged responses with these chemotherapy agents alone.
 
Recent studies have shown that in AML, the addition of a tyrosine-kinase inhibitor (TKI) to standard chemotherapy in a sequential manner is feasible and associated with anti-leukemic efficacy. A randomized study (SORAML) has shown that the addition of a sorafenib to standard chemotherapy resulted in a significantly prolonged event-free survival (EFS) and relapse-free survival (RFS). This data has also suggested that this treatment regimen can be beneficial and effective in both FLT3 (Fms-related tyrosine kinase 3) wild-type and FLT3 ITD (FLT3 – Internal Tandem Duplication) AML.
 
Crenolanib besylate is a second generation TKI with high potency and selectivity against both wild-type FLT3 and its constitutively active mutant isoforms including FLT3-ITD mutation and also tyrosine kinase domain (TKD) point mutations including the D835 TKD mutation. Clinical safety data of crenolanib is available for over 200 patients. Specifically, there are data in 66 patients with R/R FLT3 ITD and/or TKD mutant AML, which demonstrates clinical benefit in approximately 50% of these AML patients with responses that included complete remission (CR), complete remission with incomplete blood count recovery (CRi) and partial remission (PR).
 
The proposed study is designed to combine crenolanib with salvage chemotherapies, including HAM, MEC or FLAG-Ida to treat patients with R/R AML irrespective of FLT3 status. The rationale for this study is as follows:
 
 (1) There is clinical evidence for improved event-free survival in AML with the combination of a TKI and chemotherapy; (2) HAM, MEC, and FLAG-Ida have been shown to improve the outcome in patients with R/R AML;

(3) Sequential administration of chemotherapy followed by a TKI is feasible and can achieve synergistic cytotoxicity.

Study Design

Open label, dose de-escalation, phase 1b pilot trial of crenolanib with standard salvage chemotherapy. Subjects may receive up to 2 cycles of induction with standard salvage chemotherapy followed by crenolanib. Each arm will enroll approximately 24 patients (72 total); stratification to each arm will be per physician's choice.

Arm A (HAM + crenolanib)

Subjects 18-60 years of age who have not undergone a prior allogeneic hematopoietic stem cell transplant (HSCT):

- Mitoxantrone 10 mg/m² IV, over ≤ 30 mins days 1-3
- Cytarabine 1000 mg/m² IV, over 3 hours days 1-6
- Crenolanib 100 mg TID p.o. starting day 7 (+3 day)

For subjects > 60 years, or subjects who have undergone a prior allogeneic HSCT, or subjects who need a second re-induction HAM cycle, the following reduced doses will be used:

- Mitoxantrone 8 mg/m² IV, over ≤ 30 mins days 1-3
- Cytarabine 500 mg/m² IV, over 3 hours days 1-6
- Crenolanib 100 mg TID p.o. starting day 7 (+3 day)

Arm B (MEC + crenolanib)

Patients >18 years of age:

- Mitoxantrone 8 mg/m² IV, push days 1-5
- Etoposide 100 mg/m² IV days 1-5
- Cytarabine 1000 mg/m² IV, over 3 hours days 1-5
- Crenolanib 100 mg TID starting day 7 (+3 day)

Arm C (FLAG-Ida + crenolanib):

Patients >18 years of age:

- Fludarabine 30 mg/m² IV day 1-5
- Cytarabine 2 g/m² IV over 2 hrs day 1-5
- G-CSF 300 ug s.c. inj or IV/5ug/kg SC day 6 - neutrophil recovery
- Idarubicin 8 mg/m² IV over 30 min day 1-3
- Crenolanib 100 mg TID starting day 7 (+3 day)

Primary Objective

- To determine the safety, dose limiting toxicities and maximum tolerated dose (or confirm the target dose of 100 mg TID) of crenolanib given sequentially following standard salvage chemotherapy regimens in subjects with refractory/relapsed AML

Secondary Objectives

- To determine the response rate, duration of response, progression-free survival, and overall survival of crenolanib when given sequentially following standard salvage chemotherapy regimens in subjects with refractory/relapsed AML
- To determine the pharmacokinetics of crenolanib when given sequentially following standard salvage chemotherapy regimens in subjects with refractory/relapsed AML

Inclusion Criteria

1. Confirmed diagnosis of AML, including treatment-related secondary AML (except prior MDS) according to World Health Organization (WHO) 2008 classification at treating institution
2. Subjects who are refractory* or who have relapsed** following first line AML therapy with cytarabine/anthracycline based chemotherapy, with or without a tyrosine kinase inhibitor.

*Refractory to induction therapy is defined as never achieving CR, CRi or CRp (according to International Working Group criteria) after one line of intensive regimen for AML (re-induction, consolidation and/or transplant allowed) including at least one cytarabine containing induction block with a total dose no less than 700mg/m² per cycle and 3 days of an anthracycline with or without a TKI.

or

**First relapse is defined as untreated hematologic relapse (according to International Working Group criteria) after one line of intensive regimen for AML (re-induction, consolidation and/or transplant allowed) including at least one cytarabine containing induction block with a total dose no less than 700mg/m² per cycle and 3 days of an anthracycline with or without a TKI that induced a CR/CRi/CRp. Subjects are allowed to receive induction, consolidation, transplant and/or maintenance prior to achieving their first CR/CRi/CRp.

3. Subjects considered eligible for intensive chemotherapy
4. ECOG performance status ≤ 2
5. Age ≥ 18 years
6. Adequate liver function within 72 hours of enrollment, defined as:
 - Normal total serum bilirubin
 - ALT and AST $\leq 2.0 \times$ ULN
7. Adequate renal function, defined as serum creatinine $\leq 1.5 \times$ ULN
8. Women of childbearing potential must have a negative serum or urine pregnancy test with a sensitivity of at least 25 mIU/mL within 72 hours prior to enrollment

“Woman of childbearing potential” is defined as any woman who has not undergone a hysterectomy and who has had menses at any time in the preceding 24 consecutive months

9. Women of child-bearing potential must either commit to continued abstinence from heterosexual intercourse or begin one acceptable method of birth control (IUD, tubal ligation, or partner’s vasectomy) while on crenolanib and for 3 months following the last dose of crenolanib.

Hormonal contraception alone is not an acceptable method of birth control for the purpose of this trial.

10. Men must use a latex condom during any sexual contact with women of childbearing potential, even if they have undergone a successful vasectomy and must agree to avoid to father a child (while on therapy and for 3 month after the last dose of crenolanib).
11. Willing to adhere to protocol specific requirements
12. Following receipt of verbal and written information about the study, the subject must provide

signed informed consent before any study related activity is carried out.

13. Clinically significant toxic effects of prior therapy (expect hydroxyurea) resolved to Grade ≤ 1 before the start of study.

Exclusion Criteria

1. < 5% blasts in blood or marrow at screening, except if measurable extramedullary AML is confirmed
2. Acute promyelocytic leukemia (APL)
3. Known clinically active CNS leukemia
4. Clinically active or unstable graft-versus-host disease (GvHD) requiring treatment which precludes administration of chemotherapy as defined in this protocol
5. Prior anti-leukemia therapy within 14 days of enrollment for classical cytotoxic agents, and within 5x the half-life for other investigational agents
 - Prior use of hydroxyurea or isolated doses of cytarabine for palliation (i.e., control of WBC) are allowed but should be discontinued at least 24 hrs prior to enrollment.
 - Other agents used strictly with palliative intent might be allowed during this period after discussing with principal investigator
6. Pre-existing liver disease (e.g. cirrhosis, chronic hepatitis B or C, nonalcoholic steatohepatitis, sclerosing cholangitis)
7. Known HIV infection.
8. Evidence of ongoing, uncontrolled systemic infection or an uncontrolled local infection requiring therapy at the start of study.
9. "Currently active" second malignancy (other than non-melanoma skin cancer, carcinoma in situ of the cervix or prostatic intraepithelial neoplasia within 1 year). Subjects are not considered to have a "currently active" malignancy if they have completed therapy and are considered by their physician to be at less than 30% risk of relapse within 1 year.
10. Concurrent participation in another therapeutic clinical trial.
11. Pregnant or breastfeeding women
12. Subjects of childbearing potential not willing to use adequate contraception during study and 3 months after last dose of crenolanib
13. Subject with uncontrolled cardiac disease including congestive heart failure class III or IV by the NYHA, unstable angina (anginal symptoms at rest) or new onset angina (began within the last 3 months) or myocardial infarction within the past 6 months
14. Subject with concurrent severe and/or uncontrolled medical or psychiatric conditions that in the opinion of the investigator may impair the participation in the study or the evaluation of safety and/or efficacy
15. Inability to give an informed consent

Statistical Methods

Initially, the study will evaluate DLT and determine the maximum tolerated dose (or confirm the target dose of 100 mg TID) of crenolanib in combination with either HAM (Arm A), MEC (Arm B) or FLAG-Ida (Arm C) chemotherapy. Thereafter, the study will include a dose-expansion cohort.

For each arm, an initial 6 subjects will be enrolled at a crenolanib dose of 100 mg TID and will be evaluated for DLT, as follows:

- The DLT period will be 28 days
 - Assessment of potential hematologic DLTs that started during the DLT period will extend for up to 6 weeks following the start of the event (see definition of hematologic DLT)
- DLT will be defined as any clinically significant adverse event or abnormal laboratory value that

is not related to concomitant medications, co-morbidities or underlying disease (leukemia), and that is not expected for the chemotherapy being used together with crenolanib

The following will be considered to be DLT:

Non-hematologic DLT:

- Any grade 3 or 4 non-hematologic toxicity despite optimal supportive care
 - For example, grade 3 or 4 nausea, vomiting, or diarrhea that cannot be controlled with standard antiemetic or antidiarrheal medications used at optimal dose within 72 hours of onset
- Any tumor lysis syndrome

Hematologic DLT:

- Grade ≥ 3 neutropenia and/or thrombocytopenia with a hypocellular bone marrow lasting for 6 weeks or more after the last dose of therapy in the absence of residual leukemia (i.e., with less than 5% blasts)
 - Anemia will not be considered a DLT

For each arm, prior to determining the maximum tolerated dose (or confirming the target dose of 100 mg TID) of crenolanib based on DLT, subjects will be enrolled in a sequential manner such that no more than 6 subjects are within 30 days of starting induction 1 therapy. See Section 12.2.1 for dose de-escalation and stopping rules based on dose-limiting toxicity.

For each arm, following the determination of the maximum tolerated dose (or the target dose) of crenolanib, subject safety and early mortality will be monitored in cohorts of six throughout the study. Enrollment may be halted at any time based on safety reviews. See Section 12.2.2 for the study's stopping rules following the determination of the maximum tolerated dose (or the target dose) for crenolanib.

Descriptive statistics will be used to summarize the safety and efficacy data for this study. Categorical data will be summarized by number and percentage of subjects in each category. Time-to-event endpoints will be summarized using the cumulative incidence and Kaplan-Meier methodology.

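### Childbearing potential is defined by menses in the last 24 months, whatever the cause of their absence, so some premenopausal women fall outside the pregnancy-test and contraception criteria, in conflict with inclusion 9 on hormonal contraception

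*Combined protocol and SAP*

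**What the plan says.** All the relevant text is in the protocol synopsis, under Inclusion Criteria and Exclusion Criteria.

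- Definition, under inclusion 8: "any woman who has not undergone a hysterectomy and who has had menses at any time in the preceding 24 consecutive months".
- Inclusion 8: "Women of childbearing potential must have a negative serum or urine pregnancy test", within 72 hours before enrollment.
- Inclusion 9: "Women of child-bearing potential must either commit to continued abstinence from heterosexual intercourse or begin one acceptable method of birth control". The methods listed are IUD, tubal ligation and partner's vasectomy. The commitment runs until three months after the last crenolanib dose.
- Sentence directly after inclusion 9: "Hormonal contraception alone is not an acceptable method of birth control for the purpose of this trial".
- Inclusion 10: men must use a condom with women of childbearing potential and must agree not to father a child.
- Exclusion 11: "Pregnant or breastfeeding women". No test is named.
- Exclusion 12: "Subjects of childbearing potential not willing to use adequate contraception during study and 3 months after last dose of crenolanib".

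Two other criteria bear on who could be affected. Subjects are eligible from age 18. All must have had one line of intensive cytarabine and anthracycline treatment, with prior transplant allowed, and be either refractory or in first relapse. No maximum time to relapse is set.

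**The concern.** The 24-month clause appears to stand in for menopause, but as written it turns on bleeding alone. Absence of menses can have causes that do not establish that a woman cannot conceive. Long-term hormonal contraception is the plainest, and earlier leukemia treatment is another.

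At stake is the safety of a potentially fertile woman and of a pregnancy. She would receive cytotoxic chemotherapy and then crenolanib without the test and the contraception commitment that the protocol asks of other potentially fertile women. A missed period would give her no warning, because she has none to miss.

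The criteria also pull against each other. Inclusion 9 does not accept hormonal contraception as sufficient, yet the definition can exempt a woman because of what that contraception does to her menses.

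**Working it through.** The plan gives no figure to reproduce and no arithmetic applies. The check is to apply the definition to the possible cases and then trace each criterion that uses the term.

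**Step 1: the logic of the definition.** Childbearing potential = (no hysterectomy) AND (menses at some time in the preceding 24 months). If either part is false, the woman is outside the definition.

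| Case | No hysterectomy | Menses within 24 months | Inside definition | Inclusions 8 and 9 apply |
|---|---|---|---|---|
| Menstruating woman | true | true | yes | yes |
| Menses stopped less than 24 months ago, any cause | true | true | yes | yes |
| Natural menopause, 24 months or more | true | false | no | no |
| Premenopausal, menses absent 24 months on hormonal contraception | true | false | no | no |
| Premenopausal, menses absent 24 months since earlier AML therapy, now in late first relapse | true | false | no | no |
| Hysterectomy | false | any | no | no |

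Rows 3, 4 and 5 are treated alike. For row 3 that is presumably the intention. For rows 4 and 5 it is the gap.

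**Step 2: does another criterion bring rows 4 and 5 back in?**

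- *Inclusions 8 and 9* are both addressed to women of childbearing potential, so neither reaches these women.
- *The hormonal-contraception sentence* limits which methods count. It obliges nobody outside inclusion 9 to use any method.
- *Exclusion 11* applies to every woman, so a known pregnancy is excluded. It does not say how an unknown one would be found.
- *Exclusion 12* refers to subjects, not women, of childbearing potential. If the defined term governs, it does not reach rows 4 and 5. If the words carry their ordinary meaning, it does. Even then it asks only for adequate contraception and does not say what is adequate; the list of methods is in inclusion 9.
- *Inclusion 10* relies on the same phrase for men's partners. If the definition governs there too, a partner in the position of row 4 falls outside the condom requirement. The man's agreement not to father a child remains.

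**Step 3: set the two statements side by side.** Inclusion 9 treats hormonal contraception alone as insufficient. The definition treats a woman whose hormonal method has suppressed menses for 24 months as needing no contraception at all, so she may rely on that method alone. Both cannot reflect the same intention.

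**Step 4: how wide is the gap?** Menses must have been absent for the entire 24 months. A woman who menstruated until a recent diagnosis, induction or transplant is still covered (row 2). What remains is mainly suppression that began more than two years before enrollment, and first relapse at least two years after menses stopped. The criteria permit both.

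**The case against.** The strongest objection is that the rest of the protocol may close the gap. The contents list Table 3 (Screening Assessments) and Section 11.6 (Pregnancy), and neither was available to this review. If Table 3 orders a pregnancy test for all women, the missing test is supplied. This stands as a limit on the testing half of the point. It does not answer the other half, because a universal test would not put these women under the contraception requirement.

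Second, the group is small. This also stands. A reader might infer from the universal prior chemotherapy that exemption is common among younger women. The documents do not support that: absence of menses must span 24 months, which leaves out women whose menses stopped only with recent treatment. Nor do they say that menses are hormonally suppressed as part of AML care.

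Third, a reader might infer that exclusion 11 is useless and that exclusion 12 certainly does not apply. Both go too far. Exclusion 11 still removes a known pregnancy, nothing prevents an investigator from testing, and exclusion 12 can be read in its ordinary sense.

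Fourth, a correction that exempted natural menopause alone would overreach. It would bring in women with permanent ovarian failure after treatment, who would then have to meet inclusion 9 or be ineligible. This stands, and it shapes the fix.

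**Conclusion.** The concern holds for the synopsis criteria. As worded, a premenopausal woman with a uterus and no menses for the full preceding 24 months is outside inclusions 8 and 9, and exclusion 11 names no test. The conflict with the hormonal-contraception sentence follows from the text alone and needs no outside assumption.

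Its size cannot be stated. A count would multiply the roughly 72 planned subjects by the proportion who are women, the proportion of those who are premenopausal, and the proportion of those with 24 months without menses. The documents give none of these. Some of the women counted would in any case have lost fertility permanently, so such a count would not be a count of fertile women wrongly exempted. The frequency is low and the potential harm in a single case is serious, which justifies a one-clause correction.

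The conclusion assumes that investigators apply the definition as written. The part about the missing test also assumes that Table 3 and Section 11.6 do not require testing for all women.

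**What to change.** Reconcile the definition with inclusion 9:

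1. Amend the 24-month clause so that absence of menses caused by hormonal contraception or suppression, or by prior therapy without established loss of fertility, does not by itself take a woman out of the definition. Women past natural menopause, and those whose loss of fertility is established, remain exempt.
2. Use one defined term, spelled one way, in inclusions 8, 9 and 10 and exclusion 12.
3. Check Table 3 and Section 11.6 against the amended definition.

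The cost is that a few more women need the existing pregnancy test and must meet the existing contraception commitment to be eligible. The commitment is the heavier of the two, since it means abstinence or one of the listed methods until three months after the last crenolanib dose. No dose, endpoint or sample size changes.

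### Does Arm A's DLT assessment need to be split by its two HAM schedules?

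*Combined protocol and SAP*

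**What the plan says.** The Synopsis (Statistical Methods) sets out to evaluate DLTs and find the maximum tolerated dose, or confirm the target dose, of "crenolanib in combination with either HAM (Arm A), MEC (Arm B) or FLAG-Ida (Arm C) chemotherapy". The starting cohort is defined by arm: "For each arm, an initial 6 subjects will be enrolled at a crenolanib dose of 100 mg TID and will be evaluated for DLT". Until the dose is settled, the only enrolment control stated there concerns pace: "subjects will be enrolled in a sequential manner such that no more than 6 subjects are within 30 days of starting induction 1 therapy". After that, safety and early mortality are reviewed by arm in cohorts of six. The de-escalation and stopping rules are left to Sections 12.2.1 and 12.2.2.

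The Synopsis (Study Design, Arm A) gives two HAM schedules. The full one is for subjects aged 18 to 60 without a prior allogeneic transplant. The second is introduced by "For subjects > 60 years, or subjects who have undergone a prior allogeneic HSCT" and also covers "subjects who need a second re-induction HAM cycle, the following reduced doses will be used". It includes "Cytarabine 500 mg/m² IV, over 3 hours days 1-6", against 1000 mg/m² on the full schedule, and mitoxantrone at 8 instead of 10 mg/m². Crenolanib has the same dose and the same starting window on both.

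The DLT definition leaves out events linked to other causes and counts only an event "that is not expected for the chemotherapy being used together with crenolanib". Section 2.3, in the background, gives the study's cytarabine dose as 6 g/m² and does not mention the lower schedule.

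**The concern.** The primary objective is a statement about the crenolanib dose that can follow salvage chemotherapy. In Arm A that chemotherapy is not uniform, since total cytarabine differs twofold between the schedules. The entry criteria set no upper age limit and allow prior transplant, so both kinds of subject can be among the first six. The Synopsis does not control the mix and does not mention counts by schedule.

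A reader could then take a conclusion for HAM as equally well supported in older or post-transplant subjects on the reduced schedule and in the others on the full one, although one group may have contributed one or two subjects, or none. The direction of any difference is unknown, because schedule goes with age and transplant history.

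**Working it through.** **Inputs.** From the Synopsis: three arms of about 24 subjects; an initial six per arm; full HAM is mitoxantrone 10 mg/m² on 3 days and cytarabine 1000 mg/m² on 6 days; reduced HAM is 8 and 500 mg/m² on the same days. The documents do not give the share of Arm A on each schedule or any DLT rate, so both are assumed below.

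**The plan's own figures.** 3 × 24 = 72, as stated. With one infusion a day, full-schedule cytarabine is 1000 × 6 = 6000 mg/m² = 6 g/m², which matches Section 2.3.

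**Schedule totals.** Reduced cytarabine is 500 × 6 = 3 g/m². Mitoxantrone is 10 × 3 = 30 against 8 × 3 = 24 mg/m².

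**What n subjects on one schedule can show.** After zero DLTs, the one-sided 95% upper bound is 1 − 0.05^(1/n). The chance of seeing no DLT at true rate p is (1 − p)^n.

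| n on the schedule | Upper bound after 0/n | No DLT, p = 20% | No DLT, p = 1/3 | No DLT, p = 50% |
|---|---|---|---|---|
| 6 | 39% | 26% | 9% | 2% |
| 3 | 63% | 51% | 30% | 12.5% |
| 2 | 78% | 64% | 44% | 25% |
| 1 | 95% | 80% | 67% | 50% |

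With n = 0 there is no information on that schedule.

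**How uneven the first six might be.** Let K, the number on the reduced schedule, be Binomial(6, s). The chance that one schedule has at most one subject is P(K = 0, 1, 5 or 6). This is 66% for s = 20%, 43% for s = 30% and 22% for s = 50%.

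**Beyond the first six.** Arm A plans about 24 subjects. If they divided 12 and 12, zero DLTs on a schedule would give an upper bound of 1 − 0.05^(1/12) = 22%. If they divided 6 and 18, the bounds would be 39% and 15%.

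**What the arithmetic tests.** The table describes any group of that size. Counts by schedule would show which row applies, but they would not change the row, the number enrolled or any decision rule. Six is also not a fixed ceiling for the dose conclusion. The Synopsis calls the six initial, and its pace limit restricts how many subjects may be early in induction at one time, not how many may be assessed in total. The number that finally supports the conclusion depends on Section 12.2.1.

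**The case for a change.** The best case for a change is that a reassuring pooled count can hide a schedule that was barely tested. Assume DLT rates of 40% on one schedule and 10% on the other. The chance of at most one DLT in six is then 23% if all six are on the 40% schedule, 52% with a 3:3 split, and 79% if only one subject is on it. Attribution may differ as well, since what counts as expected toxicity depends on the chemotherapy given. Splitting two safety tables and adding a sentence of counts would cost almost nothing, and the counts are most useful beside the dose conclusion.

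The facts and the arithmetic stand, and showing the counts would be good reporting. The case for changing the plan does not stand, for four reasons.

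- The illustration rests on assumed rates and on an at-most-one-in-six rule that is not in the text reviewed. It bears on pooling itself, which a descriptive table leaves unchanged.
- Pooling is defensible. The drug under study has the same dose on both schedules, and the DLT definition already allows for the chemotherapy used.
- The schedule at induction 1 follows from age and transplant history, so it can be derived at any time. The descriptive safety summaries promised in the Synopsis leave room for the split. Any difference would be confounded with the same two characteristics, so it could not be read as an effect of schedule.
- The entry criteria let the same mix of age and transplant history into Arms B and C. Thin support for older or post-transplant subjects is therefore a general limit of six-subject cohorts and not a fault peculiar to Arm A.

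**Conclusion.** No change to the plan is needed. The Synopsis is silent on a tabulation that analysts can make sensibly from data needed to assign treatment, and no rule, number or decision has been shown to be wrong. An author who wishes to can list DLTs and early deaths by the HAM schedule received in induction 1, with the evaluable number on each schedule beside the Arm A dose conclusion. Induction 1 is the right basis because any second HAM cycle uses the reduced doses. This is an optional reporting choice.

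The uncertainty is real but generic: the zero-event upper bound runs from 39% with six subjects to 95% with one, and it narrows as Arm A approaches its planned 24. This conclusion assumes one infusion a day. It also allows for the fact that Section 12 was not in the text reviewed: that section may already report by schedule, or may assess more than six subjects before the dose is settled.

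Separately, the 6 g/m² in Section 2.3 matches only one of the two Arm A schedules in the Synopsis. The two passages must be reconciled, and no view is taken here on which dose is right. The sentence in Section 2.3 is background wording and has no shown effect on the analysis.
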